Statistics	
Dose Escalation:
 
During dose escalations of GEN3014, by utilizing an mBOIN, recommendations will be provided to the DEC to either escalate, remain, or de-escalate next DL in the escalation part of the trial. The mBOIN aims to characterize the DLT rate at each DL such that the RP2D (and possibly the MTD) can be determined. Escalation data will be summarized by DL and indication (RRMM or R/R AML).
 
Expansion Part A
 
The Expansion Part A will be conducted in 4 parallel cohorts:
 
 
• Anti-CD38 mAb-naïve RRMM (N=approximately 10 subjects)
 
• Anti-CD38 mAb-refractory RRMM (N=20 subjects)
 
• R/R DLBCL (up to 40 subjects): Based on a Simon's 2-stage design, up to 40 subjects with R/R DLBCL may be treated with GEN3014. The initial stage consists of 20 subjects and if least 5 of 20 subjects respond to GEN3014, the futility bar is passed.
 
• R/R AML (N=20 subjects)
 
 
The response assessment for each disease indication, for the primary endpoint of ORR, will be:
 
 
• The International Myeloma Working Group consensus criteria (IWMG) 2016 for MM,
 
• The revised response criteria for Hodgkin and non-Hodgkin lymphoma (Lugano classification) for DLBCL, and
 
• The International Working Group (IWG) response criteria for AML.
 

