## 2.2 Trial Rationale

The treatment landscape for RRMM has been dramatically changed with the approval of daratumumab first as monotherapy, followed by combinations with an IMiD or a PI. A second anti-CD38 antibody isatuximab in combination with pomalidomide or carfilzomib and dexamethasone was recently approved for RRMM. Although the clinical outcome in RRMM has been improved with anti-CD38 containing regimens, there are substantial number of patients who either relapse after or are refractory to these treatments. While endeavors are being made to understand the resistance mechanisms, it is an attractive approach to investigate a more potent agent such as GEN3014 which has a higher affinity for CD38, enhanced CDC activity and inhibition of the CD38 cyclase activity that can potentially reverse the immunosuppressive tumor microenvironment.

Preclinically, CD38-targeting GEN3014 has demonstrated more potent tumor cell killing than daratumumab across a wide panel of MM, AML, and DLBCL cell lines. In primary myeloma samples, GEN3014 showed more potent CDC activity in newly diagnosed MM. In addition, therapeutic activity of GEN3014 was observed in AML and DLBCL patient-derived xenografts (PDX) in mice in vivo.

The aim of this phase 1/2 trial is to characterize the safety, tolerability, pharmacokinetics (PK), pharmacodynamics, and preliminary anti-tumor activity of GEN3014 in subjects with RRMM and other hematologic malignancies. In the Dose Escalation, dose-limiting toxicities (DLTs) will be monitored to determine the recommended phase 2 dose (RP2D), and if reached, the maximum tolerated dose (MTD) for both RRMM and R/R AML. In the Dose Escalation, both anti-CD38 mAb-naïve RRMM and anti-CD38 mAb-treated RRMM will be enrolled. It is expected the majority of the subjects with RRMM have received prior daratumumab or daratumumab-containing regimens; and as a consequence, the baseline CD38 expression on

daratumumab-exposed myeloma cells may be relatively lower; therefore it is important to recruit anti-CD38 mAb-naïve subjects with RRMM who have abundant CD38 expression at the clinically active dose levels (eg, 16 mg/kg, 24 mg/kg) so that the safety and efficacy profile of GEN3014 can be established.

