## 9 STATISTICAL CONSIDERATIONS

The statistical analysis of the data collected in this trial is the responsibility of the sponsor. The objectives and endpoints for the 3 trial parts are tabulated in [Table 3-1](#) (Dose Escalation), [Table 3-2](#) (Expansion Part A [GEN3014 Single Cohorts]), and [Table 3-3](#) (Expansion Part B [Randomized H2H]). This section will (without particular reference to trial part) outline the planned analysis for each endpoint. The analyses will be detailed further in the Statistical Analysis Plan (SAP) to be finalized before database lock.

All presentations will be done separately for the different trial parts. Subjects in the Dose Escalation part will be analyzed according to the DL received. Subjects in Expansion Part A (GEN3014 Single Cohorts) will be analyzed according to their assigned expansion cohort. Subjects in Expansion Part B (Randomized H2H) will be analyzed according to their assigned treatment.

Statistical deliveries (tables, listings, and figures) may be produced for the following milestones:

- Periodic DMC reviews
- **Dose Escalation:** Primary safety and efficacy analyses will be conducted on all subject data at the end of the escalation, at latest 6 months after last patient first dose. Separate deliveries may be planned for the RRMM and R/R AML disease cohorts as feasible.
- **Expansion Part A (GEN3014 Single Cohorts)** consists of 4 parallel cohorts:
  - Anti-CD38 mAb-naive RRMM cohort
  - Anti-CD38 mAb-refractory RRMM cohort
  - R/R DLBCL cohort
  - R/R AML cohort

Each cohort will assess the disease-specific anti-tumor activity of GEN3014. No comparisons between cohorts are planned. Each cohort may report its individual primary analysis. The primary analyses will be conducted on all subject data, at latest 6 months after last patient first dose in respective expansion cohort. Timing of futility analyses in DLBCL cohort is described below.

- **Expansion Part B (Randomized H2H)** in anti-CD38 mAb-naive RRMM subjects: Primary safety and efficacy analyses will be conducted on all subject data, at latest 6 months after last patient first dose.
- The final analyses will be reported as an addendum to the primary analyses, based on the accumulated data up to 5 years after study start.

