## 1 INTRODUCTION

This statistical analysis plan describes in detail the analysis of the endpoints for trial GCT3014-01. GEN3014 (HexaBody®-CD38) is a fully human immunoglobulin (Ig)G1 monoclonal antibody (mAb) targeting the cluster of differentiation (CD)38 antigen. As compared to daratumumab, GEN3014 has a higher affinity for CD38, more potent CDC activity, and stronger inhibition of the CD38 cyclase activity. It is hypothesized that GEN3014 may trigger stronger reversion of the immune suppression in the tumor microenvironment.

GCT3014-01 comprises the following parts (see [Figure 1](#)):

- Phase 1 Dose Escalation Part
  - Dose escalation in RRMM
  - Dose escalation in R/R AML
- Phase 2 Expansion Part A
  - Expansion arm in anti-CD38 mAb-naïve RRMM
  - Expansion arm in anti-CD38 mAb-refractory RRMM
  - Expansion arm in R/R DLBCL
  - Expansion arm in R/R AML
- Phase 2 Expansion Part B
  - A randomized H2H comparison of GEN3014 IV versus daratumumab SC in anti-CD38 mAb-naïve RRMM

The main analysis reporting difference between the parts is the ordering of objectives and the grouping of summary statistics. In the Dose Escalation, the primary objective is to determine the safety profile (summarized by DLTs, AEs and safety laboratory parameters), while in Phase 2 Expansion it is to further characterize the antitumor activity based on disease specific response evaluations:

- The International Myeloma Working Group consensus criteria (IWMG) 2016 for RRMM,
- The revised response criteria 2014 for Hodgkin and non-Hodgkin lymphoma (Lugano classification) for R/R DLBCL, and
- The International Working Group (IWG) 2003 response criteria for R/R AML.

The grouping factor in Dose Escalation is the dose level per disease type while in Phase 2 Expansion the results will be summarized by the (disease) cohort. Besides this and the different disease specific response criteria, the underlying details of the analyses and the statistical methodologies do not differ between escalation and expansion, or between diseases. This SAP is thus used for both parts, with above differences noted. To ease the presentation of the planned analysis, the word “cohort” will be used throughout, but this can also be thought of as the dose level in Dose Escalation. Layouts, programming notes and titles for the tables, listings and figures are further specified in the Data Presentation Specification (DPS).

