### **5.3.4      *Supplementary Analyses***

To explore the treatment effect while trial is ongoing, the ORR may be presented also for the RES.

Due to the low sample size, no subgroup analyses are planned.

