**Table 9: PK parameters**

AUC 0-last	Area under the plasma concentration-time curve, from time zero to the last quantifiable concentration (mass x time x volume  )
AUC inf	Area under the plasma concentration time curve from time zero to infinity (mass x time x volume  )
C max	Maximum observed drug concentration in plasma after each administration (mass x volume  )
t max	Time of maximum observed concentration (time)
t 1/2	The elimination half-life associated with the terminal slope of a semi logarithmic concentration-time curve (time)

CL	Apparent total plasma clearance (volume x time  )
C trough	Observed pre-dose drug concentration

Additional parameters such as dose normalized Cmax and AUCs, apparent volume of distribution, accumulation ratios may be calculated to fully characterize the PK profiles of GEN3014.

All subjects in the PAS 1 for which PK parameters can be calculated will be included in the summaries. Descriptive statistics provided will include the number of subjects, arithmetic mean, standard deviation (SD), arithmetic coefficient of variation, reported as a percentage (CV%), median, minimum, and maximum. Geometric mean and geometric CV% will be calculated for continuous PK parameters. Tmax will be presented as median, minimum, and maximum.

Dose-response between dose and PK parameters will be presented. Associations between PK parameters and covariates such as weight, age, as well as relationships between emerging observations of safety, efficacy or pharmacodynamic biomarkers and plasma exposure may be explored graphically by the sponsor, possibly outside the scope of this SAP depending on the findings.

If deemed applicable, compartmental modelling approaches may be performed by the sponsor outside of the scope of this SAP.

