#### **5.6.5 Subgroup Analyses**

Due to the heterogeneous population, and expected low sample size within each disease type, there are no subgroup analyses planned for the escalation stage.

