#### **6.4.1 *RRMM disease specific characteristics***

- Subtype of MM disease (IgA, IgD, IgG, IgM, Light Chain)
- Serum M-protein level (summary statistics)
- Urine M-protein level (summary statistics)
- Number of plasmacytomas (summarized by 0 or  $\geq 1$ )
- Number of lytic lesions (None, 1-3, 4-10, > 10, Unable to Determine)
- Percentage bone marrow plasma cells (<5,  $\geq 5$  - <10,  $\geq 10$  - <30,  $\geq 30$  - <60,  $\geq 60$ , Missing)
- ISS stage at screening (Stage I, Stage II, Stage III, Missing)
- Anti-CD38 mAb-naïve (yes or no)
- Time since last anti-CD38 treatment (summary statistics)

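### Myeloma Dose Escalation efficacy is summarised by dose level without separating anti-CD38-naive from anti-CD38-treated subjects, although naive subjects are preferentially sought at the active doses, so case mix alone can produce a response gradient.

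*Protocol*

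**What the plan says.** The grouping of escalation results is consistent across the two documents. The synopsis says "Escalation data will be summarized by DL and indication (RRMM or R/R AML". Protocol Section 9 says "Subjects in the Dose Escalation part will be analyzed according to the DL received". SAP Section 1 says "The grouping factor in Dose Escalation is the dose level per disease type".

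No further split is planned. SAP 5.3.4, on ORR, says "Due to the low sample size, no subgroup analyses are planned". SAP 5.6.5 says "there are no subgroup analyses planned for the escalation stage", giving the mixed population and small numbers as the reason.

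On recruitment, Protocol 2.2 expects most myeloma escalation subjects to have had daratumumab, which may leave their myeloma cells with relatively low CD38. It then says that "it is important to recruit anti-CD38 mAb-naïve subjects with RRMM who have abundant CD38 expression at the clinically active dose levels", with 16 and 24 mg/kg as examples. Protocol 4.1 counts naive subjects treated at those two doses in the escalation toward the 10-subject lead-in for the head-to-head part. Protocol 4.1.1 allows naive subjects in the myeloma escalation with no dose-level limit.

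Prior exposure is recorded: SAP 6.4.1 lists "Anti-CD38 mAb-naïve (yes or no" as a baseline characteristic. For pharmacokinetics, SAP 5.6.1.2 says "Dose-response between dose and PK parameters will be presented". It names weight and age as covariates that may be explored, but not prior anti-CD38 exposure.

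**The concern.** If naive subjects cluster at the higher doses and respond more often, dose level stands in for prior exposure in every by-dose efficacy summary. A reader of the ORR table would see response climbing with dose and could not tell how much of the climb comes from the drug and how much from who was enrolled.

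The plan treats the two groups as distinct populations elsewhere: Expansion Part A has separate naive and refractory myeloma cohorts. Protocol Table 3-1 makes ORR, CBR, DOR, TTR, PFS and OS secondary endpoints of the escalation and makes the dose-concentration-response relationship an exploratory objective. Those are the results at stake.

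**Working it through.** **The plan's own figure.** Protocol 9.5.1 gives 95% for at least 2 responders among 10 naive subjects at a true ORR of 40%. Exactly: 1 − 0.6^10 − 10 × 0.4 × 0.6^9 = 1 − 0.0060 − 0.0403 = 0.954. It reproduces, and 40% is taken as the naive ORR. Protocol 2.1.1.1, with about 60% of patients not responding to daratumumab, agrees with that.

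**Inputs that the documents do not give.** The ORR in treated subjects (p), the naive share at low doses (f_low) and at 16–24 mg/kg (f_high), and the numbers treated. All are assumed over a range.

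**Expected false rise.** With no dose effect in either group, ORR at a dose level is 0.40f + p(1 − f), so the rise is (f_high − f_low) × (0.40 − p).

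| p | f_low | f_high | Rise |
|---|---|---|---|
| 0.15 | 0.10 | 0.50 | 0.40 × 0.25 = 0.10 |
| 0.10 | 0 | 0.70 | 0.70 × 0.30 = 0.21 (10% versus 31%) |
| 0 | 0 | 0.80 | 0.80 × 0.40 = 0.32 |

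Over p of 0 to 15%, f_low of 0 to 10% and f_high of 50 to 80%, the range is 10 to 32 points. A milder case outside that grid (p = 20%, f_low = 20%, f_high = 50%) gives 0.30 × 0.20 = 6 points. The rise is zero if the naive shares are equal or if p is also 40%.

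**Chance of an observed rise of at least 20 points.** Take 8 subjects at 8 mg/kg and below, which is the minimum in Protocol Table 4-1 (1 + 1 + 3 + 3), and 20 at 16–24 mg/kg, which is assumed. Let p = 10% and put no naive subjects at low doses. Low-dose responders are Binomial(8, 0.10). High-dose responders are the sum of Binomial(k, 0.40) and Binomial(20 − k, 0.10), where k is the number of naive subjects. The probabilities are exact. The balanced column gives both dose groups the overall ORR, for example (14 × 0.40 + 14 × 0.10)/28 = 0.25 for k = 14.

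| Naive share at high dose (k) | Naive share overall | P(rise ≥ 20 points) | Balanced case mix |
|---|---|---|---|
| 30% (6) | 6/28 = 21% | 0.26 | 0.11 |
| 50% (10) | 10/28 = 36% | 0.42 | 0.13 |
| 70% (14) | 14/28 = 50% | 0.58 | 0.15 |

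At a 70% share the figure is 0.70 for p = 5% and 0.48 for p = 15%. At a 50% share with p = 20% it is 0.31. With group sizes of 6 and 18 and p = 10%, it is 0.42 at half naive and 0.62 at three-quarters naive.

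**Pharmacokinetics.** Protocol 4.3.1.1 expects target-mediated clearance to lessen as malignant cells are lysed, and Protocol 2.2 describes naive subjects as CD38-rich. More naive subjects at the top doses would then tend to lower dose-normalised exposure there. The documents give no exposure or clearance values by CD38 status, so no size can be computed.

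**The case against.** The case for leaving the plan alone has real content.

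- **Small numbers, stated choice.** Initial dose levels hold 1 or 3 subjects and the escalation algorithm allows at most 9 per level. No hypotheses are tested, and escalation efficacy is secondary. This stands: any split can only be descriptive.
- **Other views of prior exposure exist.** Naive status and time since last anti-CD38 treatment are in the baseline table, baseline CD38 is tabulated and may be correlated with response, individual responses are listed, the lead-in reviews naive subjects at the active doses, and Part A has separate naive and refractory cohorts. These help, but none is an escalation table of response by dose within prior-exposure group, and the lead-in has no low-dose comparator.
- **The imbalance is unknown.** The doses in Protocol 2.2 are examples, and lower doses are open to naive subjects. A 70% share at high dose makes half of the 28 subjects naive, which sits badly with the expectation that most are daratumumab-exposed. The 30% and 50% rows fit that expectation better.
- **The low-versus-high contrast is a construct.** The planned tables are by individual dose level. The contrast measures what a reader would see across their rows.

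Three stronger readings are tempting but not supported. A reader might infer that pharmacokinetic exposure would also rise falsely with dose. It rises with mg/kg dose by construction, and the case-mix distortion of dose-normalised exposure probably runs the other way. A reader might infer that the RP2D rests on this artefact. Protocol 4.1.2.5 bases it on the totality of data, Protocol 4.3.2 records 16 mg/kg as chosen, and both example doses in Protocol 2.2 are named together, so that text implies no imbalance between them. A reader might infer that infusion reactions differ by prior exposure; the documents do not say so.

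**Conclusion.** The concern holds for efficacy. Following the plan as written, the myeloma escalation tables of ORR, CBR, DOR and PFS can show a dose gradient produced by prior-exposure case mix. The false rise in ORR is 10 to 32 points over the main range, and smaller if naive subjects are spread more evenly or treated subjects respond more often. Only the 40% naive ORR comes from the documents; the treated ORR, naive shares and high-dose numbers are assumptions. Dose-normalised pharmacokinetics is also confounded, probably in the opposite direction and by an unknown amount. Because the RP2D is already set, the consequence is limited to how the escalation secondary endpoints and the exploratory dose-concentration-response displays will be read.

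**What to change.** In SAP 5.3–5.4, 5.6.1 and 5.6.5:

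- Present myeloma Dose Escalation efficacy by dose level within prior anti-CD38 status (naive / treated), labelled descriptive.
- Draw the dose-response displays, including those for pharmacokinetics, within the same two groups.
- Keep the pooled by-dose tables, and add the number of naive subjects at each dose level.
- Make an exception for this one variable to the no-subgroup statements in SAP 5.3.4 and 5.6.5.

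The variable is already collected, so the cost is SAP wording and extra table columns. The drawback is very small cells, many with only a few subjects and some empty, so the split tables can show whether a gradient persists within a group but cannot estimate it with any precision.

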## 1.2 Schema

**Figure 1-1 Schematic Overview of the Trial**

\*R/R AML cohort to be opened after GEN3014 has been tested in DL of 16 mg/kg in RRMM

DL=dose level; IA=interim analysis; IV=intravenous; MTD=maximum tolerated dose; RP2D=recommended phase 2 dose; RRMM=relapsed or refractory multiple myeloma; R/R AML=relapsed or refractory acute myeloid leukemia; R/R DLBCL=relapsed or refractory diffuse large B-cell lymphoma; SC=subcutaneous

### 1.3 Schedule of Activities

Table 1-1 through Table 1-15 list all of the assessments and indicate with an “X” the evaluations performed by visit.

#### Dose Escalation:

- Table 1-1 Schedule of Activities – Subjects With RRMM – Dose Escalation
- Table 1-2 Schedule of Activities – Subjects With R/R AML – Dose Escalation
- Table 1-3 Schedule for PK, Biomarker/Pharmacodynamic, and Immunogenicity Sampling – All Subjects – Dose Escalation
- Table 1-4 Minimal Residual Disease CCI Evaluation Schedule – Subjects with RRMM – Dose Escalation

#### Expansion:

- Table 1-5 Schedule of Activities – Subjects With RRMM – Expansion Part A (GEN3014 Single Cohorts)
- Table 1-6 Schedule of Activities – Subjects With R/R AML – Expansion Part A (GEN3014 Single Cohorts)
- Table 1-7 Schedule of Activities – Subjects With R/R DLBCL – Expansion Part A (GEN3014 Single Cohorts)
- Table 1-8 Schedule for PK, Biomarker/Pharmacodynamic, and Immunogenicity Sampling – All Subjects – Expansion Part A (GEN3014 Single Cohorts)
- Table 1-9 Minimal Residual Disease CCI Evaluation Schedule – Subjects with RRMM – Expansion Part A (GEN3014 Single Cohorts)
- Table 1-10 Minimal Residual Disease Schedule – Subjects with R/R AML – Expansion Part A (GEN3014 Single Cohorts)
- Table 1-11 Minimal Residual Disease CCI Evaluation Schedule – Subjects with R/R DLBCL – Expansion Part A (GEN3014 Single Cohorts)
- Table 1-12 Schedule of Activities – Subjects with RRMM – Expansion Part B (Randomized H2H)
- Table 1-13 Schedule for PK, Biomarker/Pharmacodynamic, and Immunogenicity Sampling – GEN3014 IV-Treated Subjects – Expansion Part B (Randomized H2H)
- Table 1-14 Schedule for PK, Biomarker/Pharmacodynamic, and Immunogenicity Sampling – Daratumumab SC-Treated Subjects – Expansion Part B (Randomized H2H)
- Table 1-15 Minimal Residual Disease CCI Evaluation Schedule – Subjects with RRMM – Expansion Part B (Randomized H2H)

In addition to the fixed visits, it may be necessary to perform some of the assessments at unscheduled time points if deemed clinically necessary by the investigator.

**Table 1-1 Schedule of Activities – Subjects With RRMM – Dose Escalation**

				Q1W (Weekly)						Q2W		Q4W	UNS	End of Treat- ment	Safety Follow- up 	Survival Status/ contact 
	Pro- tocol Section	Notes	Screen- ing	Cycle 1-2						Cycles 3-6		Cycle 7 onward				
Cycle(s)			D -21 to D -1	D1 	D2 (C1 only)	D8	D9  (C1 only)	D15	D22	D1	D15	D1		ASAP after last dose	30d after last dose	Q3M
Visit Window								±3d		±3d		±3d		+7d	+7d	±7d
Informed consent	10.1.5	Obtain prior to any trial-related activity	X													
Eligibility criteria	5.1, 5.2		X													
Demographics	8.1.1		X													
Medical history 	8.1.3		X 	X												
Disease status	8.1.2	Includes diagnosis and staging criteria	X													
Constitutional symptoms	8.3.7	At Screening and before GEN3014 dosing	X	X		X		X	X	X	X	X				
ECOG PS	8.3.5		X	X						X		X	X	X		
Prior anti-cancer therapy	6.7.1		X													
Prior/concomitant medications and therapies	6.7		X	X	X	X	X 	X	X	X	X	X	X	X		
Height	8.3.2		X													
Body weight	8.3.2	Measure weight within 72 h before GEN3014 infusion	X	X		X		X	X	X	X	X	X			

				Q1W (Weekly)						Q2W		Q4W	UNS	End of Treatment	Safety Follow-up 	Survival Status/contact 
Cycle(s)	Pro- tocol Section	Notes	Screen- ing	Cycle 1-2						Cycles 3-6		Cycle 7 onward				
Cycle Day			D -21 to D -1	D1 	D2 (C1 only)	D8	D9  (C1 only)	D15	D22	D1	D15	D1		ASAP after last dose	30d after last dose	Q3M
Visit Window								±3d		±3d		±3d		+7d	+7d	±7d
Vital signs	8.3.3	On GEN3014 dosing days, as per Section 8.3.3. At Safety Follow-up visit as required per local health authorities (see Section 10.15).	X	X	X	X	X 	X	X	X	X	X	X	X	X	
Physical examination	8.3.1	At Screening, perform complete physical exam. At subsequent visits, a symptom-directed/ clinically indicated (brief) physical examination may be performed. At Safety Follow-up visit as required per local health authorities (see Section 10.15).	X	X						X		X		X	X	
12-Lead ECG	8.3.4	Perform in triplicate	X	X		X		X	X	X	X	X	X	X		
Adverse Events 	8.4		X 	X	X	X	X	X	X	X	X	X	X	X	X 	
TRIAL DRUG ADMINISTRATION																
Post-infusion monitoring 	4.1.1.2			X  (C1)	X 	X  (C1)	X  (C1)	X  (C1)	X  (C1)							

				Q1W (Weekly)						Q2W		Q4W	UNS	End of Treat- ment	Safety Follow- up 	Survival Status/ contact 
Cycle(s)	Pro- tocol Section	Notes	Screen- ing	Cycle 1-2						Cycles 3-6		Cycle 7 onward				
Cycle Day			D -21 to D -1	D1 	D2 (C1 only)	D8	D9  (C1 only)	D15	D22	D1	D15	D1		ASAP after last dose	30d after last dose	Q3M
Visit Window								±3d		±3d		±3d		+7d	+7d	±7d
Pre-infusion and post-infusion medication	6.2	Pre- and post- infusion medications required before all GEN3014 infusions.		X	X	X	X 	X	X	X	X	X				
GEN3014 administration	4.1.1, 4.1.1.1	C1D1 dose is split between 2 consecutive days (C1D1 and C1D2).		X 	X 	X 	X 	X	X	X	X	X				
LOCAL LABORATORY ASSESSMENTS																
Hematology	8.3.6	Also see Table 10-1. At Safety Follow-up visit as required per local health authorities (see Section 10.15).	X	X	X	X	X 	X	X	X	X	X	X	X	X	
Biochemistry	8.3.6	Also see Table 10-1. At Safety Follow-up visit as required per local health authorities (see Section 10.15).	X	X	X	X	X 	X	X	X	X	X	X	X	X	
Coagulation	8.3.6	Also see Table 10-1	X	X	X	X	X 	X	X	X	X	X	X	X		
Urinalysis	8.3.6	Also see Table 10-1	X	X						X		X	X	X		
β2-microglobulin	8.3.6	Also see Table 10-1	X													
Pregnancy test (serum or urine)	8.3.6	Also see Table 10-1 Serum pregnancy test at Screening. Subsequent tests can be serum or urine. Confirm negative	X	X						X		X	X	X		

				Q1W (Weekly)						Q2W		Q4W	UNS	End of Treat- ment	Safety Follow-up 	Survival Status/ contact 
Cycle(s)	Pro- tocol Section	Notes	Screen- ing	Cycle 1-2						Cycles 3-6		Cycle 7 onward				
Cycle Day			D -21 to D -1	D1 	D2 (C1 only)	D8	D9  (C1 only)	D15	D22	D1	D15	D1		ASAP after last dose	30d after last dose	Q3M
Visit Window								±3d		±3d		±3d		+7d	+7d	±7d
		result before dosing.														
HBV and HCV serology	8.3.6	Also see Table 10-1	X													
HIV serology	8.3.6	Performed at Screening only if required per local health authorities or institutional standards (see Section 10.15.1 ).	X													
CMV serology	8.3.6	Also see Table 10-1	X													
TLS	8.3.6, 10.3.7	Also see Table 10-1 . Use Cairo-Bishop Grading System.	X	X	X	X	X 	X	X	X (C3)			X			
Blood type assessment	8.3.6.3	Also see Table 10-1	X													

				Q1W (Weekly)						Q2W		Q4W	UNS	End of Treat- ment	Safety Follow-up 	Survival Status/ contact 
Cycle(s)	Pro- tocol Section	Notes	Screen- ing	Cycle 1-2						Cycles 3-6		Cycle 7 onward				
Cycle Day			D -21 to D -1	D1 	D2 (C1 only)	D8	D9  (C1 only)	D15	D22	D1	D15	D1		ASAP after last dose	30d after last dose	Q3M
Visit Window								±3d		±3d		±3d		+7d	+7d	±7d
Cytogenetics	8.1.2.1, 8.3.6.1	Also see Table 10-1	X													
Molecular mutational status	8.1.2.1, 8.3.6.1	Also see Table 10-1	X													
CENTRAL LABORATORY																
PK	8.6		See Table 1-3													
ADA	8.9															
Biomarkers	8.8															
MRD CCI	8.8		See Table 1-4													
MM DISEASE: ASSESSMENTS INCLUDING CENTRAL AND LOCAL LABORATORY ASSESSMENTS																
Quantitative serum Ig panel	8.2.1.1, 8.3.6.2	All subjects will be evaluated for IgG, IgA, IgM, IgE, and IgD at Screening. Also see Table 10-1 .	X													
SPEP and UPEP (24-h urine sample) and interference assay sample 	8.2.1.1, 8.3.6.4	Perform Screening SPEP and UPEP within 14 days prior to C1D1. Also see Table 10-1 .	X 	X 						X 		X 	X	X 		
Serum FLC and serum/urine IFE 	8.2.1.1, 8.3.6.4	Also see Table 10-1 .	X	X 						X 		X 	X	X 		
Serum calcium corrected for albumin	8.2.1.2, 10.7	Also see Table 10-1 .	X	X						X		X	X	X		

				Q1W (Weekly)						Q2W		Q4W	UNS	End of Treat- ment	Safety Follow-up 	Survival Status/ contact 
Cycle(s)	Pro- tocol Section	Notes	Screen- ing	Cycle 1-2						Cycles 3-6		Cycle 7 onward				
Cycle Day			D -21 to D -1	D1 	D2 (C1 only)	D8	D9  (C1 only)	D15	D22	D1	D15	D1		ASAP after last dose	30d after last dose	Q3M
Visit Window								±3d		±3d		±3d		+7d	+7d	±7d
Skeletal survey 	8.2.1.5	Low-dose whole body CT is preferred. Depending on local practice, a skeletal survey by x-ray or MRI may be used as an alternative.	X 	As clinically indicated 												
Bone marrow aspirate  and/or bone marrow biopsy	8.2.1.3	Needed to confirm CR/sCR, assess MRD, and for biomarker evaluations (see Table 1-3)	X 	Collect at C4D1 ±7 days for all subjects, and at time of suspected CR/sCR. Also collect at 6, 12, 18, 24 and 30 (±1) months post C1D1 for subjects who achieve CR/sCR and remain on trial. At investigator's discretion, may be repeated if clinically indicated. 									X			
Assess extramedullary plasmacytomas 	8.2.1.4	Subject with history of plasmacytomas, or if clinically indicated at Screening.	X 	Measure every 4 weeks for physical examination (if applicable) and every 12 weeks for imaging assessment 									X			
Response Assessment	8.2.1	To be performed starting C2D1		X (C2)						X		X	X	X		
END OF TREATMENT																
New anti-cancer therapy	7.1.1														X	X
Survival Status	7.1.2															X

ADA=anti-drug antibody; AE=adverse event; ASAP=as soon as possible; C=cycle; CMV=cytomegalovirus; CR=complete remission; CT=computed tomography; CCI=central nervous system; D/d=day; ECG=electrocardiogram; ECOG PS=Eastern Cooperative Oncology Group performance status; FLC=free light chain; FFPE=formalin-fixed, paraffin-embedded; h=hour(s); HBV=hepatitis B virus; HCV=hepatitis C virus; HIV=human immunodeficiency virus; ICF=informed consent form; IFE=immunofixation; Ig=immunoglobulin; min=minute(s); IRR=infusion-related reaction; MRD=minimal residual disease; MRI=magnetic resonance imaging; PD=progressive disease; PK=pharmacokinetic(s); Q3M=every 3 months; Q1W=every week;

Q2W=every 2 weeks; Q4W=every 4 weeks; RRMM=relapsed or refractory multiple myeloma; SAE=serious adverse event; sCR=stringent complete response; SPEP=serum protein electrophoresis; TLS=tumor lysis syndrome; UNS=unscheduled; UPEP=urine protein electrophoresis.

1. Subjects discontinuing from treatment for any reason will have a safety follow-up visit 30 days (+7 days) after the last dose of GEN3014. If the subject initiates new anti-cancer therapy within 30 days of the last dose of GEN3014, the safety follow-up visit should be performed prior to starting new anti-cancer therapy. Once new anti-cancer treatment is initiated, the subject will move into survival status follow-up.
2. Subjects will enter the survival follow-up after completion of the safety follow-up or if new anti-cancer treatment has been started. Survival follow-up contact may be performed as a telephone call, email, or on-site visit.
3. Baseline is defined as the available data from the latest recorded measurement made before the first GEN3014 administration.
4. To be performed at Cycle 1 Day 9 only for the MM-DL1 cohort (who is receiving a split dose on Days 8 and 9).
5. Any medical condition (signs, symptoms, and diagnosis) or procedures occurring prior to first GEN3014 dose should be documented as medical history. Medical conditions that occur after the ICF is signed and prior to first GEN3014 dose should only be reported as AEs if they were assessed by the investigator to be caused by a protocol-mandated procedure (ie, tumor biopsy and/or CT scan), including washout or discontinuation of prior medications.
6. Only SAEs judged by the investigator as related to GEN3014 should be reported after the safety follow-up period.
7. During Cycle 1, subjects in the first 2 dose levels (MM-DL1 and MM-DL2) are required to remain in the clinic for at least 8 hours after each GEN3014 infusion so that they can be observed closely. During treatment Cycle 1, all other subjects must be observed after each GEN3014 infusion for at least 4 hours. Additional or longer monitoring is permissible per the investigator's discretion. If a subject has an IRR of  $\geq$  grade 3 during any infusion, the subject will be required to stay overnight following the infusion.
8. For MM Dose Level 1 (MM-DL1), during Cycle 1, the C1D1 first dose is split between C1D1 and C1D2; the C1D8 second (escalated) dose is split between C1D8 and C1D9; the full dose is administered on C1D15, C1D22, and all dosing days for subsequent cycles. For MM-DL2 and subsequent cohorts, during Cycle 1, the C1D1 dose is split between C1D1 and C1D2; the full dose is administered on C1D8, C1D15, C1D22, and all dosing days for subsequent cycles.
9. SPEP and UPEP must be performed within 14 days prior to C1D1, and on C1D1. If Screening assessment performed within 3 days prior to C1D1, it is not necessary to repeat at C1D1. Subsequent on-treatment SPEP and UPEP are to be performed every 28 ( $\pm$ 3) days on the scheduled assessment day. All responses based on biochemical investigations, including PD, require 2 consecutive assessments by local lab for confirmation. Once PD is confirmed, subsequent disease assessments are not required. Additional aliquots will be collected for IFE reflex testing, in case of potential interference of GEN3014 with interpretation of M-protein levels.
10. Perform serum FLC and serum/urine IFE when CR is suspected or maintained. To confirm CR, undetectable M-protein electrophoresis studies in both serum and urine will trigger central laboratory to perform IFE studies in both serum and urine and FLC in serum. Perform serum FLC on Day 1 of every cycle for all subjects.
11. A skeletal survey, including cranium, is required during Screening. Results from skeletal survey performed within 42 days before C1D1 as routine follow up for subject's disease state may be used. Additional imaging will be performed as clinically indicated.
12. At baseline (Screening) only, non-decalcified diagnostic slides (bone marrow aspirate, touch preparation or clot selection) or FFPE block (clot section only, no bone marrow biopsy) up to 42 days prior to enrollment may be collected for MRD assessment if the fresh aspirate fails to calibrate during testing.
13. To confirm CR/sCR, assess MRD, and for other biomarker evaluations. Samples to be collected at C4D1  $\pm$ 7 days for all subjects. Also collect samples at time of suspected CR/sCR, and at 6, 12, 18, 24 and 30 ( $\pm$ 1) months post C1D1 for subjects who achieve CR/sCR and remain on trial. If 1 of these time points occurs within 1 month of suspected CR, a repeat bone marrow will not be requested. The bone marrow tests for CR/sCR and beyond will only be required if subject's response is near CR or better by blood and urine evaluations.
14. Extramedullary plasmacytomas should be assessed for all subjects with a history of plasmacytomas or if clinically indicated at Screening, by clinical examination or radiologic imaging. Results from radiologic plasmacytoma assessment performed within 42 days before C1D1 as routine follow up for subject's disease state may be used. Imaging methodology used for evaluation should be consistent across all visits. Irradiated or excised lesions will be considered not measurable, and will only be monitored for PD.

